2.0 INTRODUCTION AND LITERATURE REVIEW

2.1 Introduction

Rhinitis is a condition of the nasal cavity in which the membrane lining the nasal cavity becomes irritated and swollen. Patients typically present with complaints of runny nose, itchy or watery eyes, sneezing, irritated throat and postnasal discharge. Rhinitis may be caused by allergens (such as pollen, pet dander, mold or dust), or by other triggers (including chemicals, irritants, and medications).¹

Chronic rhinitis may significantly impact a patient's quality of life by causing fatigue, headache, and sleep disturbance, resulting in cognitive impairment and diminished productivity and thereby posing both a personal and financial burden.²

2.2 Nasal Anatomy

The nose is a respiratory organ that performs a prominent airflow regulatory role. Air enters the nasal cavity, where it is warmed to a temperature of approximately 31° C to 34° C, regardless of the outside temperature. The nose also humidifies the inspired air to a relative humidity of 90% to $95\%^3$. These functions prevent drying of the distal airways, which allows optimal gas exchange, and helps maintain healthy body temperature. In addition to these heating and humidification roles, the nose serves to protect the airway by filtering inhaled particulates.⁴

The nasal cavity is covered with an epithelial lining made of cells which interact to serve appropriate functions in the nasal environment. Cells located in the epithelial lining include ciliated cells, goblet cells and seromucous glands. The serous cell contributes to the seromucous glands that moisten membranes, the ciliated cells produce the fine hairs that move foreign substances out of the airway and the goblet cell produces a carbohydrate called mucin which attracts water and forms a gelatin-like substance better known as mucus.^{5,6}

The goblet cell is the most prominent mucus producing cell in the nasal membrane and together with the seromucous glands, works to provide the mucus fluid on the nasal surface. The purpose of mucus is to protect the body from substances that can enter through the nasal cavity. Secretion is stimulated by dust or foreign substances that enter the nasal passage. As a natural defense it is then cleared by movement of the cilia and disposed to the stomach.⁶

Regulation of the seromucous glands and blood supply occurs through parasympathetic and adrenergic stimulation via the vidian nerve, posterior nasal nerves and other nerves. In some situations, the mucosa may become hyperresponsive to stimuli, and produce excess mucus, resulting in rhinorrhea or postnasal discharge.

Do not copy, distribute, or share with others without prior written authorization from Aerin Medical Inc.

3.0 RHINITIS DIAGNOSIS AND TREATMENT

3.1 Diagnosis

Patients presenting with runny or congested nose, watery eyes, irritated throat and/or sneezing symptoms are evaluated to understand the types of triggers that may prompt the symptoms experienced. By having patients complete a quality of life and symptom questionnaire during the history and physical exam, the practitioner will better understand the duration, course and suspected cause of symptoms. This questionnaire typically asks patients to describe certain environmental factors that may trigger the allergy symptoms. Respiratory irritants may help differentiate if the symptoms relate to allergic or non-allergic responses.^{2,7,8} One algorithm for evaluating rhinitis patients is presented in Figure 1.¹

TP668	Ver.	27-NOV-2018
--------------	------	-------------

CONFIDENTIAL

8 of 43

3.1.1 Transnasal Endoscopy

Physicians observe the nasal structures by transnasal endoscopy to rule out anatomic conditions mimicking rhinitis. A small scope with a camera attached is inserted into each nostril to observe the nasal cavity. Common anatomical obstructions that may cause rhinitis-like symptoms are nasal polyps, deviated septum, foreign bodies, nasal tumors and turbinate hypertropy.^{1,2} Treatment of these anatomical causes, if present, may relieve rhinitis symptoms.

3.1.2 Allergy Testing

The most common methods to determine allergy sensitivity are percutaneous skin testing and the allergen-specific immunoglobulin E (IgE) antibody testing. These tests can identify allergens the patient should avoid. However, if an allergic cause is eliminated through this testing, a diagnosis of nonallergic rhinitis could be made.^{1,2}

3.2 Treatment

3.2.1 Medical Treatment

Nasal irrigation (nasal lavage) may reduce symptoms if done multiple times a day with a saline rinse. Allergic rhinitis patients usually find relief with use of over-the-counter oral or nasal antihistamines and/or corticosteroid sprays and may only require administration at specific times of the year.² Allergen immunotherapy may also be effective in treating allergic rhinitis.

Patients with nonallergic rhinitis are less likely to respond to oral antihistamines, but may find their symptoms relieved with intranasal antihistamine, corticosteroid or anticholinergic sprays.

Patients whose symptoms are not adequately relieved with conservative treatment usually seek further management to alleviate symptoms and may be candidates for nasal surgery.

3.2.2 Surgical Treatment – Neurectomy

Vidian neurectomy is a surgical option to relieve nasal symptoms as the vidian nerve supplies autonomic input to nasal mucosa (as well as the palate and the lacrimal gland). While this surgery has been performed for over 50 years, it is known to be highly controversial since access to the nerve proves to be technically difficult and complications with numerous surrounding important structures can occur.^{9,10} Common procedural side effects include dry eyes, nasal dryness or crusting and mild pain, whereas more significant risks may include hemorrhage, vision loss and palate/lip/cheek numbness. In addition, improvement in symptoms is often unpredictable.⁹

An alternative neurectomy target is the posterior nasal nerve (PNN). The advantage of the PNN over the vidian nerve is its more limited innervation (it primarily stimulates the nasal mucosa) and its physical distance from other major nerve structures. As a result,

complications associated with PNN surgery are less significant and occur less frequently than those described for vidian nerve neurectomy,⁹ while still providing significant improvement in quality of life.¹¹

A recent publication describes the use of a cryosurgical probe to ablate posterior nasal nerve tissue.¹² This article details the long-term (1 year) results of treatment in a population of 27 chronic rhinitis patients, of which 48% had allergic rhinitis. Significant improvement in total nasal symptom score was seen between baseline score and each follow-up visit. Post-procedure adverse events resolved or improved by the 30-day follow-up visit. Overall, 74% of subjects had symptom improvement by 6 months post-procedure.

4.0 CURRENT USE OF RADIOFREQUENCY ENERGY IN THE NOSE

Radiofrequency (RF) energy has been used for decades in the fields of otorhinolaryngology, neurosurgery, cardiology, urology and general surgery.

ENT surgeons currently use radiofrequency energy daily in numerous nasal therapies. Radiofrequency turbinate reduction (RFTR), for instance, is a minimally invasive surgical option that can reduce tissue volume in a precise, targeted manner. This technique uses radiofrequency energy to create heat within the submucosal tissue of the turbinate, reducing tissue volume with minimal impact on surrounding tissues.¹³ Radiofrequency turbinate reduction differs fundamentally from traditional surgical methods by using low-power radiofrequency energy to provide a relatively quick and painless procedure for tissue coagulation and/or ablation.

There have been multiple studies analyzing the safety and outcomes of using radiofrequency energy in the RFTR procedure. In 2009, Hytonen, et al.¹⁴ completed a systematic literature review of the RFTR technique and concluded that the technique is well tolerated and effective.

Numerous studies have demonstrated that radiofrequency tissue therapy in the nasal passage can be safe and effective in improving nasal obstruction and in preserving nasal function¹⁵. Kezirian et al.¹⁶ reported 1 minor complication of crusting in 89 adult patients treated with radiofrequency ablation of the turbinates. The same authors also reported no moderate or major complications after RFTR based on a review of published literature results.

5.0 STUDY RATIONALE

Aerin Medical previously conducted a small feasibility study (TP220) using the Aerin Medical radiofrequency system to treat subjects with chronic rhinitis. The InSeca Stylus was used to apply radiofrequency energy to the inferior turbinate. At 6-months postprocedure, 73% of subjects showed improvement in their Sino-Nasal Outcomes (SNOT-22) score. There were no device-related or procedure-related serious adverse events.

The current study is intended to further evaluate the use of the InSeca Stylus for treating rhinitis by targeting treatment to the portion of the inferior turbinate mucosa overlying the region of the posterior nasal nerve.

6.0 SUMMARY DEVICE DESCRIPTION

The Aerin Medical InSeca ARC System (Figure 2) includes two FDA-cleared products: the InSeca ARC Stylus (Figure 3), which is a disposable handheld device capable of delivering bipolar radiofrequency energy to tissue, and the Aerin Medical Console (Figure 4), a temperature-controlled generator that delivers low doses of radiofrequency energy to the Stylus. The Stylus is attached to the Aerin Medical Console via a flexible cable. The Stylus has received FDA clearance for "the coagulation of soft tissue in the nasal airway, to treat nasal airway obstruction by shrinking submucosal tissue."

The InSeca ARC Stylus consists of a handle, shaft and treatment tip. The tip (Figure 5) comprises two rows of electrodes placed on either side of a non-conductive mold. A probe located in the center of the tip between the two electrode rows contains a thermocouple that constantly measures the temperature of the tissue, providing feedback to the generator and allowing the generator to automatically adjust energy delivery as necessary. The stylus tip is temporarily inserted into the nose to deliver low-power RF energy to the treatment area. It generates heat within the submucosal tissue and creates a coagulation lesion. The stylus may be used to treat multiple locations in one or both nostrils of a single patient. If the straight InSeca ARC Stylus cannot access the target treatment area, the Stylus may be bent using the Oratec Probe Bender (Figure 6). The Stylus should only be manipulated in the bender one time and should not be bent more than 20 degrees.

Figure 2. InSeca ARC Stylus with Aerin Console

Figure 3. InSeca ARC Stylus (not to scale)

Figure 4. Aerin Medical Console

TP668 Ver. 27-NOV-2018

CONFIDENTIAL

14 of 43

Figure 5. InSeca ARC Stylus Treatment Tip (not to scale)

Figure 6. Oratec Probe Bender With InSeca ARC Stylus

 TP668 Ver. 27-NOV-2018
 CONFIDENTIAL

 This document contains proprietary and confidential information of Aerin Medical, Inc.
 Do not copy, distribute, or share with others without prior written authorization from Aerin Medical Inc.

7.0 STUDY DESIGN AND ENROLLMENT

7.1 Study Design and Objectives

This study is a prospective, multicenter, nonrandomized, nonsignificant risk (NSR) study of the Aerin Medical InSeca ARC Stylus. The primary objective of this study is to evaluate treatment outcomes when the InSeca ARC System is used to treat the posterior nasal nerve area of the nasal passageway to improve symptoms in adults diagnosed with chronic rhinitis.

The design encompasses a 2-phase enrollment. Up to 10 subjects will be enrolled in the first phase. Further enrollment will be suspended until all initial subjects have completed their 4-week evaluation. Information from these patients will be used to assure the safety of the procedure as well as the adequacy of treatment settings and treatment locations.

7.2 Subject Population

The population being targeted for this therapy consists of patients who have exhibited symptoms of chronic rhinitis for at least six months. To evaluate the severity of a patient's rhinitis symptoms both before and after the procedure, this study will use the 4-item Total Nasal Symptom Scale (TNSS). The maximum TNSS score is 12 and indicates the most severe symptoms. Aerin Medical has chosen a baseline 12-hour reflective TNSS (a 12-hour rTNSS) score of at least 6 for inclusion in the study, with the additional requirements that the subject have at least moderate (score of 2) rhinorrhea symptoms and at least mild (score of 1) congestion.

Patients who have anatomic obstructions that may limit access to the target treatment area or have altered posterior nasal anatomy due to prior surgery or injury are excluded from participation.

Eligible subjects must meet the inclusion and exclusion criteria described in Sections 7.3 and 7.4. Any questions regarding a potential subject's eligibility for enrollment must be discussed with the Sponsor prior to scheduling the subject for the procedure.

7.3 Inclusion Criteria

To be eligible to participate in this study, a patient must meet all the following criteria:

- 1. Age 22 to 75 years (inclusively)
- 2. Willing and able to provide informed consent
- 3. Willing and able to comply with the subject-specific requirements outlined in the study protocol
- 4. Seeking treatment for chronic rhinitis symptoms of at least 6 months duration and willing to undergo an office-based procedure
- 5. Moderate to severe symptoms of rhinorrhea (rTNSS rating of 2 or 3 for rhinorrhea)
- 6. Mild to severe symptoms of nasal congestion (rTNSS rating of 1, 2 or 3 for congestion)
- 7. rTNSS score of ≥ 6
- 8. Dissatisfaction with medical management, defined as usage of intranasal steroids for a minimum of 4 weeks without adequate symptom relief, as judged by the subject

7.4 Exclusion Criteria

A patient who meets any of the following criteria is not eligible to participate in the study:

- 1. Anatomic obstructions that in the investigator's opinion limit access to the posterior nose
- 2. Altered anatomy of the posterior nose as a result of prior sinus or nasal surgery or injury
- 3. Active nasal or sinus infection
- 4. Moderate to severe ocular allergic symptoms (such as eye tearing [epiphora], itching [pruritus], or redness [erythema])
- 5. History of significant dry eye
- 6. History of any of the following: nose bleeds in the past 3 months, rhinitis medicamentosa, head or neck irradiation
- 7. Known or suspected allergies or contraindications to the anesthetic agents and/or antibiotic medications to be used during the study procedure session
- 8. Known or suspected to be pregnant, or is lactating
- 9. Participating in another clinical research study
- 10. Other medical conditions which in the opinion of the investigator would predispose the subject to poor wound healing, increased surgical risk, or poor compliance with the requirements of the study

8.0 STUDY PHASES

The study will be conducted in four phases as subjects are consented, evaluated for eligibility, treated and followed until study exit:

Phase 1 - Pre-Screen / Informed Consent Process

- Phase 2 Screening / Baseline Evaluation
- Phase 3 Enrollment / Study Procedure
- Phase 4 Follow-up / Study Exit

The different study phases are described in Sections 8.1 through 8.4. Section 8.5 provides a table of required study visits, the visit windows, and the assessments to be done at each visit, as well as a description of each assessment type.

8.1 Phase 1: Pre-Screen and Informed Consent Process

Patients presenting with symptoms associated with rhinitis will be approached with the study and asked if they are willing to volunteer participation. Patients will initially be asked about duration of symptoms and conservative measures used for their condition. Any known concomitant nasal conditions and past nasal surgeries or injuries will be discussed to understand if they are potential candidates for the study.

Informed Consent

Informed consent will be obtained as outlined in 21 CFR Part 50 and the Good Clinical Practice E6(R2): Integrated Addendum to ICH E6(R1) (March 2018).

A research study member at the approved study site will speak with the study candidate about the purpose of the study. Explanation of the study background, study procedure (including risks and benefits), and follow up visit schedule will be reviewed in detail with the patient. Patients will be given the time they need to read through the study information and informed consent document and ask as many questions as necessary to make them comfortable with the study and the requirements. For those potential candidates who agree to participate in the study by signing the IRB-approved Informed Consent Form (ICF), a baseline evaluation will be conducted.

8.2 Phase 2: Screening and Baseline Evaluation

During the screening/baseline visit in the study clinic, the Investigator or designated research staff will perform a formal evaluation of the study candidate for study eligibility, which will include a

history and physical examination of the nasal area, review of overall medical history, understanding of general health and discussion of any conservative measures used for rhinitis.

The following data will be collected:

- Patient demographics
- Medical history including prior tests and treatments for rhinitis
- Current medications and conditions for which they are prescribed
- Physical exam and vital signs
- Reflective TNSS questionnaire (symptom severity over the preceding 12 hours as reported by the subject)
- Investigator visual assessment (using an endoscope) of the target treatment area (posterior nasal nerve area) and any anatomy that might hamper necessary device access

Subjects who agree to participate and meet the enrollment criteria must be scheduled to undergo the study procedure **within 4 weeks** of the baseline visit.

8.4 Phase 4: Follow-Up and Study Exit

The follow-up period begins after the study procedure session. Subjects will undergo follow-up visits at **2 weeks**, **4 weeks**, **12 weeks**, **26 weeks and 52 weeks**, calculated from the study procedure date. Visits should be scheduled within the visit windows specified in Table 1. Requirements for each follow-up visit are described in Section 8.5 and shown in Table 1.

Subjects meeting the study requirements as planned will be exited from the study at the 52-week follow up visit. If a subject reaches the 52-week follow-up visit and is experiencing a new or ongoing adverse event, the study sponsor should be contacted to discuss the need and/or methods for continued surveillance of the event.

8.5 Types of Assessments

The following assessments will be obtained from the study subjects at the specified study follow-up visits:

Total Nasal Symptom Score (TNSS) – The TNSS is an instrument used to collect patient selfrated severity of four nasal symptoms: rhinorrhea, nasal congestion, nasal itching and sneezing. The FDA cites this as a preferred measure of efficacy in trials of drug treatments for allergic rhinitis¹⁷ and nonallergic rhinitis¹⁸. The TNSS requires the subject to rate four nasal symptoms (rhinorrhea, nasal congestion, nasal itching and sneezing) on the following 4-point scale:

- 0 = absent symptoms (no sign/symptom is evident)
- 1 = mild symptom (sign/symptom present, but minimal awareness; easily tolerated)
- 2 = moderate symptoms (definite awareness of sign/symptom that is bothersome but tolerable)
- 3 = severe symptoms (sign/symptoms that is hard to tolerate; causes interference with activities of daily living and/or sleeping)

For the purposes of this study, the subject will be asked to evaluate symptom severity over the preceding 12 hours.

Do not copy, distribute, or share with others without prior written authorization from Aerin Medical Inc.

Visual Assessment of Treatment Area – The target posterior nasal nerve area within each nostril will be visually assessed at baseline and following the treatment procedure at the time points described in Table 1. The use of an endoscope for visual assessment is required. For consistency in reporting across sites, a study CRF will outline specific observations to be assessed.

Video should be captured and archived during the endoscopic evaluation. These videos will allow for future evaluation or comparison, if necessary. If video capture is unavailable, representative still photographs may be collected instead.

Visual Analog Scale (VAS) for Pain Intensity¹⁹ – The Pain VAS will be used to rate pain associated with the treatment (i.e., in the treatment area) immediately following the procedure and at each follow-up visit through 12 weeks. Subjects will be asked to mark their pain level on a 10-cm line anchored by verbal descriptors: 0 = no pain and 10 = worst pain imaginable. The study staff will measure with a metric ruler from the 0, the beginning of the line, to the vertical mark made by the subject. The result, expressed in millimeters, will represent the subject's VAS Pain Score.

Study-Specific Quality of Life (QOL) Questionnaire – The QOL questionnaire will be used to gain understanding of the impact of chronic rhinitis on the subject's daily activities, feelings, symptoms and medication use. The QOL will be completed by the subject both prior to the treatment procedure, and at the 12-week, 26-week and 52-week follow-up visits.

Subject Satisfaction Survey – The Satisfaction Survey will be used to assess patient acceptance of the treatment procedure and results. Subjects will be asked to complete the Satisfaction Survey at the 12-week and 52-week follow-up visits.

Adverse Event Evaluation – Subjects will be asked about possible side effects or adverse experiences related to the study procedure. All events will be documented on the Adverse Event Log and Adverse Event Case Report Form. Anticipated observations related to the study procedure will be tabulated but will not be categorized as adverse events unless they require mitigation by the treating physician or are greater in severity, duration or degree of incidence than anticipated. Refer to Table 2 for a listing of anticipated observations as well as anticipated frequency, severity and duration.

Medications – Updates to current medications and any new or changed medications will be requested at each follow-up visit. The medication log will be updated to reflect any changes. In addition, any medications required as a result of intervention related to the study procedure will be documented and correlated with the Adverse Event Case Report Form.

Table 1 outlines the assessments to be performed at each required visit and specifies the required visit windows.

TP668 Ver. 27-NOV-2018

Assessments	Screening / Baseline	Study Procedure (within 4 weeks of Baseline visit)	Immediately Post- Treatment	2-Week Follow-Up (+/- 3 days)	4-Week Follow-Up (+/- 1 week)	12-Week Follow-Up (+/- 2 weeks)	26-Week Follow-Up (+/- 3 weeks)	52-Week Follow-Up (+/- 4 weeks)
Demographics and Medical History	Х							
Physical Exam and Vital Signs	Х							
Medication Review	Х	Х		Х	Х	Х	Х	Х
Study Procedure		Х						
Endoscopic Assessment of treatment area (with video or photo capture)	Х	X*	X*	Х	Х	Х	Х	Х
rTNSS Score	Х			Х	Х	Х	Х	Х
Subjective Pain VAS			Х	Х	Х	Х		
QOL Questionnaire	Х					Х	Х	Х
Subject Satisfaction Survey						Х		Х
Adverse Event review			Х	Х	Х	Х	Х	Х
Pregnancy test (if female)		Х						

*Endoscopic assessment to be done both immediately prior to and after procedure

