12.1 Potential Risks

Potential risks associated with the use of the InSeca ARC System do not differ from those of the commonly used devices and procedures to treat chronic rhinitis discussed previously, but due to the non-surgical nature of the therapy, small treatment area, low-power delivery and lack of need for general anesthesia, the overall risk to the patient may be less than from other procedures such as vidian neurectomy, septoplasty and/or functional rhinoplasty.

Potential risks associated with the use of the InSeca System and/or the associated local anesthetics are outlined below. Subjects will be monitored closely as part of this study to allow for detection of symptoms, should they be present. This, in turn, should allow for early treatment or intervention, if necessary.

The following are adverse events or side effects that may occur as a result of the treatment:

- Infection
- Bleeding (other than intra-treatment at treatment sites and greater than anticipated by the investigator)
- Mucosal changes
- Scar formation leading to nasal obstruction •
- Sensory changes at treatment site •
- Dry eye •
- External swelling of nose •
- Vasovagal response secondary to the procedure •
- Change in external shape or appearance of nose •

The following two tables list anticipated observations that are expected in and around the treatment Table 2 provides the incidence (reported as percentage of treated nostrils) observed in area. Clinical Study TP258, the nasal valve pivotal study. Table 3 provides the incidence observed in Clinical Study TP220, the rhinitis feasibility study. Anticipated observations will be assessed and recorded at study visits if they occur but, being anticipated as a result of the procedure, will not be considered adverse events unless they require mitigation by the treating physician or are greater in severity, duration or degree of incidence than anticipated. If one of these types of observations is deemed to be an adverse event, it should be recorded on the study Adverse Event CRF.

Observation	Post-Procee (% treated ne n = 99)	dure ostrils	4-Week Follow-Up (% treated nostrils n = 99)		12-Week Foll (% treated no n = 99)	ow-Up ostrils	26-Week Foll (% treated no n = 96)	ow-Up ostrils
Inflammation / redness	Not present Mild Moderate	53 42 5	Not present Mild Moderate	79 17 4	Not present Mild Moderate	89 9 2	Not present Mild Moderate	89 10 1

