Swelling, edema	Not present Mild Moderate	45 52 3	Not present Mild Moderate	75 24 1	Not present Mild Moderate	89 9 2	Not present Mild Moderate	89 8 3
Nasal obstruction from tissue edema	Not present Mild Moderate	76 23 1	Not present Mild Moderate	82 13 5	Not present Mild	94 6	Not present Mild Moderate	90 9 1
Disruption of mucosal flow / crusting	Not present Mild Moderate	89 10 1	Not present Mild Moderate	62 34 4	Not present Mild Moderate	84 15 1	Not present Mild Moderate	91 8 1
Blanching	Not present Mild Moderate	29 58 13	Not present Mild	98 2	Not present Mild	98 2	Not present	100
Numbness	Not present Mild Moderate	56 30 14	Not present	100	Not present	100	Not present	100
Soreness, pain	Not present Mild Moderate	70 29 1	Not present Mild	94 6	Not present Mild	99 1	Not present	100
Bleeding at anesthetic injection site (no intervention)	Not present Mild Moderate	51 47 2	Not present	100	Not present	100	Not present	100
Bleeding at treatment site (no intervention)	Not present Mild	85 15	Not present	100	Not present	100	Not present	100
Saddle nose deformity	Not present	100	Not present	100	Not present	100	Not present	100
Bruising around orbital area	Not present	100	Not present	100	Not present	100	Not present	100

Table 2. Treatment Area Observations – TP258 Nasal Valve Pivotal Clinical Study

Table 3. Treatment Area Observations - TP220 Rhinitis Feasibility Clinical Study

Observation	Baseline (% treated nostrils n = 22)	Baseline2-Week Follow-Up $\%$ treated nostrils(% treated nostrils $n = 22$) $n = 20$)		1-Month Follo (% treated no n = 16)	ow-Up strils	3-Month Follow-Up (% treated nostrils n = 8)	
Swelling, edema	Not present9Mild91	Not present Mild	75 25	Not present Mild Not reported	75 12.5 12.5	Not present Mild	75 25
Blanching / color of mucosa	Pale pink 100	Pale pink Hyperemic	90 10	Pale pink	100	Pale pink Not reported	75 25
Obstruction	Not present91Present beyondmid-Meatus9	Not present Present in Ethmoid	90 10	Not present	100	Not present	100
Discharge	Not present45.4Thin36.4Thick18.2	Not present Thin Thick	60 35 5	Not present Thin	87.5 12.5	Not present Thin	87.5 12.5
Scarring / Crusting	Not present 91 Mild 9	Not present Mild Severe	35 50 15	Not present Mild	62.5 37.5	Not present	100

TP668 Ver. 27-NOV-2018

CONFIDENTIAL

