13.12 Other Safety Analyses

13.12.1 Nasal Status Assessment

Each component of the assessment will be summarized as frequency and percentage for each level of the categorical variable at baseline and each follow-up evaluation.

TP668 Ver. 27-NOV-2018

CONFIDENTIAL

30 of 43

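### Three wording conflicts affect the descriptive adverse-event summary: the question put to subjects, the denominator, and the benchmark for anticipated findings

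*Combined protocol and SAP*

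**What the plan says.** **Question put to subjects.** Section 8.5 (Adverse Event Evaluation) is the only place that says what subjects are asked, and it limits the question to effects or experiences connected with the procedure. Section 31.0 defines an AE as any untoward occurrence and notes that no relationship to the device is implied. Section 11.0 leaves the judgement of relatedness to the investigator. Section 13.11 analyses all AEs and summarises their relationship to device and procedure.

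**Denominator.** Section 13.11 describes events from the procedure onward but takes every enrolled subject as the analysis set. Under 8.3 a subject is enrolled on arrival at the clinic, before treatment. Section 13.7 foresees subjects who are enrolled and not treated. Section 13.4 defines a Safety Population of treated subjects.

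**Benchmark.** Sections 8.5 and 12.1 share one rule: an anticipated observation is tabulated but is not an AE unless it needs mitigation, "or are greater in severity, duration or degree of incidence than anticipated". They differ on where the anticipated observations are listed. Section 8.5: "Refer to Table 2 for a listing of anticipated observations as well as anticipated frequency, severity and duration". Section 12.1: "The following two tables list anticipated observations that are expected in and around the treatment" area, meaning Table 2 (TP258, nasal valve study) and "Table 3. Treatment Area Observations - TP220 Rhinitis Feasibility Clinical Study". Section 12.1 also has a separate bulleted list of potential adverse events, which includes mucosal changes and scarring that obstructs the nose.

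**The concern.** The type and frequency of AEs is the named primary safety endpoint. If subjects screen their own events for relatedness before reporting them, some events never reach the investigator, who is meant to make that judgement. If people who were never exposed to the device stay in the denominator, the percentages are diluted. If two sections give different lists of expected findings, sites (up to 10) can classify the same finding differently depending on which section they follow.

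The data are also used during the trial. Enrolment pauses after up to 10 subjects, until their 4-week evaluation, so that safety can be reviewed (7.1, 13.1). That period includes the 2-week visit, where the two tables diverge.

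**Working it through.** The safety endpoint has no hypothesis and no numerical target, so there is no figure in the plan to reproduce. The check compares passages, with simple counts.

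**1. Question against definition**

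| Step | Section | Scope |
|---|---|---|
| Subject is asked | 8.5 | procedure-related experiences |
| Event qualifies as an AE | 31.0 | any cause |
| Relatedness is judged | 11.0 | by the investigator, for each AE |
| AEs are analysed | 13.11 | all AEs, with relatedness summarised |

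The first step is narrower than the three that follow it. The documents give no basis for estimating how many events would be lost.

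**2. Denominator**

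- Entry to the enrolled set: arrival at the clinic (8.3). The pregnancy test is at the procedure visit (Table 1), so a subject can be enrolled and then found unsuitable for treatment.
- First scheduled AE review: immediately after treatment (Table 1). An enrolled subject who is not treated therefore has no scheduled AE review but still counts in the 13.11 denominator.
- Use of the Safety Population: defined in 13.4, named in no analysis.
- Size, with N = 50 enrolled, x = 10 subjects with an AE (assumed) and u untreated (assumed). Enrolled basis: x/N = 10/50 = 20.0%. Treated basis, x/(N − u):
  - u = 1: 10/49 = 20.4%
  - u = 2: 10/48 = 20.8%
  - u = 5: 10/45 = 22.2%
- The shift is 0.4 to 0.8 percentage points for one or two untreated subjects, and 2.2 points for five.

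**3. Benchmark**

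| | Table 2 (TP258) | Table 3 (TP220) |
|---|---|---|
| Cited in 8.5 | yes | no |
| Cited in 12.1 | yes | yes |
| Post-treatment columns | post-procedure, 4, 12, 26 weeks | 2 weeks, 1 month, 3 months |
| Highest grade in any row | Moderate | Severe |

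The Severe grade is in the row "Scarring / Crusting" at 2 weeks: 35% not present, 50% mild, 15% severe. These add to 100% of 20 nostrils, so severe = 0.15 × 20 = 3 nostrils. The row is a composite and does not say whether scarring or crusting was severe.

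Take a severe finding of this kind at 2 weeks that needs no mitigation. Under 8.5 the list is Table 2, where nothing is graded above Moderate, so the finding exceeds the anticipated severity and is an AE. Under 12.1 the list includes Table 3, where that grade was seen at that visit, so the finding need not be an AE. Section 12.1's own list of potential adverse events, which names obstructive scarring, adds a third reference for the same kind of finding.

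**The case against.** The strongest reply is that little is lost in practice. Section 8.5 goes on to require that all events be documented, and 11.0 requires each AE to be recorded. Medication review and endoscopy at every follow-up visit offer other ways for an event to surface. Section 13.11 states one denominator explicitly, and no passage prescribes another. The 8.5 reference to Table 2 does not say that Table 2 alone applies, and Table 2 has no 2-week column, so calling the severe finding an AE under 8.5 relies on Table 2's other visits. Anticipated observations are tabulated either way, and 13.12.1 adds: "Each component of the assessment will be summarized as frequency and percentage for each level of the categorical variable".

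Most of this stands, and it limits the size of the point. It does not remove it. An event that is never mentioned cannot be documented, and neither medication review nor endoscopy will find every unrelated event. One stated denominator can still be a poor one when it includes unexposed people with no scheduled AE review. An incomplete cross-reference matters when it sits in the section that tells sites how to evaluate AEs.

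Three stronger readings are tempting, and the documents do not support them.

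- *The AE summary has no unique definition.* The question in 8.5 affects completeness, not definition, and 13.11 gives a single denominator. Only the benchmark allows two classifications, and only for some findings.
- *The tables set conflicting incidence thresholds.* The row "Swelling, edema" totals 11% at 12 weeks in Table 2 (9 + 2) and 25% at 3 months in Table 3 (2 of 8 nostrils). But Table 3 shows mild swelling in 91% of 22 nostrils at baseline, so its 25% is a fall from baseline, and Table 2 gives no baseline. Incidence is also a group quantity and cannot classify a single finding.
- *The 15% severe rate predicts a count in this trial.* Section 5.0 says of TP220: "The InSeca Stylus was used to apply radiofrequency energy to the inferior turbinate". The area in 8.3 is described differently, nostrils are paired within subjects, and Table 3 does not say how many findings needed mitigation.

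**Conclusion.** The point holds as three wording conflicts that affect the descriptive all-AE summary. No hypothesis test, error rate or sample size changes, and the serious and unanticipated event types listed in 13.11 should be little affected.

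- **Question:** a real mismatch. Its effect cannot be quantified from the documents and is reduced by the other routes of detection.
- **Denominator:** a small dilution, 20.0% against 20.4% to 20.8%, assuming 10 subjects with an AE and one or two untreated among 50.
- **Benchmark:** a severe unmitigated finding at 2 weeks may be an AE under one section and not under the other. The number of findings affected in this trial cannot be estimated.

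The wording should be corrected because this is a primary endpoint and the changes are cheap. The numerical consequence is modest.

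**What to change.** 1. **Section 8.5, question.** Delete the qualifier that restricts the AE question to procedure-related experiences. Relatedness then rests with the investigator, as in 11.0.
2. **Section 13.11, analysis set.** Replace the enrolled set with the Safety Population of 13.4, and list separately any events in subjects who were enrolled but not treated, including events during anesthesia. Align 11.0 with this: for events between baseline and treatment it names only the medical record, so it should say how such events in enrolled subjects reach the listing.
3. **Sections 8.5 and 12.1, benchmark.** Reconcile the two passages, together with 12.1's list of potential adverse events, so that all cite the same benchmark. Which benchmark applies is for the sponsor to decide. The text should also say what applies at visits the benchmark does not cover; neither table reaches 52 weeks.

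Cost: wording in 8.5, 11.0, 12.1 and 13.11, and slightly more events to log. No visit or test is added.
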